6.3.6 Ophthalmologic examination

Full ophthalmic assessment, including slit lamp examination, should be performed at screening and if a patient experiences any visual symptoms (including blurring of vision) with additional tests if clinically indicated. Ophthalmology examination results should be collected in the eCRF.

Any clinically significant findings, including those confirmed by the ophthalmologist must be reported as an AE. Photographs should be performed to record any clinically significant findings. These photographs should be available for central review by AstraZeneca and AstraZeneca representatives if necessary.

Patients experiencing corneal ulceration will not be permitted to restart study treatment.

6.3.7 Echocardiogram/MUGA Scan

An Echocardiogram or MUGA scan to assess LVEF will be performed at screening (prior to first dose of AZD9291) and every 12 weeks relative to first dose. The modality of the cardiac function assessments must be consistent within a patient i.e., if echocardiogram is used for the screening assessment then echocardiogram should also be used for subsequent scans. The patients should also be examined using the same machine and operator whenever possible.

6.3.8 Follow-up

6.3.8.1 Discontinuation Visit

A discontinuation Visit will be performed at the time of AZD9291 is permanently stopped. Refer to the study plan (Table 2) for full details.

6.3.8.2 Safety Follow-Up

In addition for safety follow-up as a minimum, telephone contact should be made with the patient 28 days following the discontinuation of AZD9291 to follow-up on any SAE/AE's and concomitant medications (including any subsequent cancer therapy). Any SAE will be followed to resolution where possible (Refer to Study Plan Table 2).

6.4 Adverse events

The Principal Investigator is responsible for ensuring that all staff involved in the study is familiar with the content of this section.

6.4.1 Definition of adverse events

An adverse event is the development of an undesirable medical condition or the deterioration of a pre-existing medical condition following or during exposure to a pharmaceutical product, whether or not considered causally related to the product. An undesirable medical condition can be symptoms (eg, nausea, chest pain), signs (eg, tachycardia, enlarged liver) or the abnormal results of an investigation (eg, laboratory findings, electrocardiogram). In clinical

studies, an AE can include an undesirable medical condition occurring at any time, including run-in or washout periods, even if no study treatment has been administered.

Any deterioration of the disease under study and associated symptoms or findings should not be regarded as an adverse event as far as the deterioration can be anticipated (see Section 6.4.3).

The term adverse event is used generally to include any AE whether serious or non-serious.

6.4.2 Definitions of serious adverse events

A serious adverse event (SAE) is an AE occurring during any study phase (ie, run-in, treatment, washout, follow-up), that fulfils one or more of the following criteria:

- Results in death
- Is immediately life-threatening
- Requires in-patient hospitalisation or prolongation of existing hospitalization
- Results in persistent or significant disability/ incapacity or substantial disruption of the ability to conduct normal life functions
- Is or results in a congenital abnormality or birth defect
- Is an important medical event that may jeopardise the patient or may require medical intervention to prevent one of the outcomes listed above.

For further guidance on the definition of a SAE, see Appendix G of this Clinical Study Protocol.

For definition of other significant adverse events (OAE) see Section 7.3.1.

6.4.3 Recording of adverse events

Time period for collection of adverse events

AEs will be collected throughout the study, from informed consent until the end of the follow up period. The follow-up period is defined as 28 days after study treatment is discontinued. SAEs occurring in the follow-up period should be reported to AstraZeneca in the usual manner (see Section 6.4.4).

Following discontinuation of AZD9291, SAEs considered related to study procedures should continue to be collected while patients are followed up for disease progression, as outlined in Table 3.

	Consent to Treatment Period	Until 28-day Follow- up Visit (safety follow-up period)	Post 28-day Follow-up visit
Collect all new AEs in eCRF	Yes	Yes	No
Collect all ongoing AEs in eCRF	Yes	Yes	No
Collect all study procedure- related SAEs in eCRF	Yes	Yes	Yes
Death due to AE, or unknown cause	Yes	Yes	No

Table 3 Summary of recording and follow-up of adverse events and deaths

After the final database lock, there may be some patients remaining on study treatment. For these patients who are continuing to receive AZD9291, AZ will collect information (during the treatment period and for 28 days after last dose) on SAEs, deaths (including those due to disease progression), discontinuation due to AEs/SAEs and drug accountability only.

Follow-up of unresolved adverse events

Any AEs that are unresolved at the patient's last visit (28-day follow-up visit) in the study are followed up by the investigator for as long as medically indicated. AstraZeneca retains the right to request additional information for any patient with ongoing AE(s) at the end of the study, if judged necessary.

If an investigator learns of any SAEs, including death, at any time after a patient has completed the study and he/she considers there is a reasonable possibility that the event is related to AZD9291, the investigator should notify AstraZeneca.

Variables

The following variables will be collected for each AE:

- AE diagnosis/description
- The date when the AE started and stopped
- Changes in CTCAE grade (for skin reactions and diarrhoea only); maximum CTCAE grade for all other AEs
- Whether the AE is serious or not
- Investigator causality rating against the investigational product (yes or no)

- Action taken with regard to investigational product
- Outcome

For SAEs other variables will be collected including treatment given for the event.

It is important to distinguish between serious and severe AEs. Severity is a measure of intensity whereas seriousness is defined by the criteria in Section 6.4.2. An AE of severe intensity need not necessarily be considered serious. For example, nausea that persists for several hours may be considered severe nausea, but not a SAE. On the other hand, a stroke that results in only a limited degree of disability may be considered a mild stroke but would be an SAE.

The grading scales found in the current National Cancer Institute CTCAE version 4 will be utilised for all events with an assigned CTCAE grading. For those events without assigned CTCAE grades, the recommendation in the CTCAE criteria that converts mild, moderate and severe events into CTCAE grades should be used. A copy of the current CTCAE version can be downloaded from the Cancer Therapy Evaluation Program website (http://ctep.cancer.gov).

Causality collection

The investigator will assess causal relationship between investigational product and each adverse event, and answer 'yes' or 'no' to the question: 'Do you consider that there is a reasonable possibility that the event may have been caused by the investigational product?'

For SAEs causal relationship will also be assessed for other medication and study procedure. Note that for SAEs that could be associated with any study procedure the causal relationship is implied as 'yes'.

A guide to the interpretation of the causality question is found in Appendix B of this Clinical Study Protocol.

Adverse events based on signs and symptoms

All AEs spontaneously reported by the patient or care provider or reported in response to the open question from the study personnel: 'Have you had any health problems since the previous visit/you were last asked?', or revealed by observation will be collected and recorded in the eCRF. When collecting AEs, the recording of diagnoses is preferred (when possible) to recording a list of signs and symptoms. However, if a diagnosis is known and there are other signs or symptoms that are not generally part of the diagnosis, the diagnosis and each sign or symptom will be recorded separately.

Adverse events based on examinations and tests

The results from protocol mandated laboratory tests, vital signs, ECGs and other safety assessments will be summarised in the CSR. Deterioration as compared to baseline in these parameters will therefore only be reported as AEs if they fulfil any of the criteria for an SAE,

a DLT or are the reason for discontinuation of treatment with the investigational product unless clearly due to progression of disease under study (see Disease progression).

If deterioration in a laboratory value, vital sign, ECG or other safety assessment is associated with clinical signs and symptoms, the sign or symptom will be reported as an AE and the associated laboratory result or other finding will be considered as additional information. Wherever possible the reporting investigator uses the clinical, rather than the laboratory term (eg, anaemia versus low haemoglobin value). In the absence of clinical signs and symptoms, clinically relevant deteriorations in non-mandated parameters should be reported as AE(s).

Deterioration of a laboratory value that is unequivocally due to disease progression should not be reported as an AE.

Any new or aggravated clinically relevant abnormal medical finding at a physical examination as compared with the baseline assessment will be reported as an AE.

Disease progression

Disease progression can be considered as a worsening of a patient's condition attributable to the disease for which the investigational product is being studied. It may be an increase in the severity of the disease under study and/or increases in the symptoms of the disease. The development of new, or progression of existing metastasis to the primary cancer under study should be considered as disease progression and not an AE. Events that are unequivocally due to disease progression should not be reported as AEs during the study.

New cancers

The development of a new cancer should be regarded as an AE and will generally meet at least one of the serious criteria. New cancers are those that are not the primary reason for the administration of the study treatment and have been identified after the patient's inclusion in this study. They do not include metastases of the original cancer.

Handling of deaths

All deaths that occur during the study, or within the follow-up period after the administration of the last dose of investigational product, should be reported as follows:

- Death, which is unequivocally due to disease progression, should be communicated to the study monitor at the next monitoring visit and should be documented in the eCRF module, but should not be reported as a SAE during the study.
- Where death is not clearly due to disease progression of the disease under study the AE causing the death should be reported to the study monitor as an SAE within 24 hours. The report should contain a comment regarding the co-involvement of progression of disease, if appropriate, and should assign a single primary cause of death together with any contributory causes.

• Deaths with an unknown cause should always be reported as a SAE but every effort should be made to establish a cause of death. A post-mortem may be helpful in the assessment of the cause of death, and if performed a copy of the post-mortem results (with translation of important parts into English) should be reported in an expedited fashion to an AstraZeneca representative within the usual timeframes

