6. STUDY PLAN AND COLLECTION OF STUDY VARIABLES

6.1 Study Plan

Table 2Study Plan

Study Plan 40 & 80 mg tablet cohort

	Screening	Sing (7 d	gle dose ay cycl	e /Cycl e)	le O		Mult Cycle	iple I e 1 (2	Dosing/ 1 Day (cycle)	Cycle 2 – Cycle 4 (21 Day Cycle)	Cycle 2 only	Cycle 5 onwards (21 Day cycle)	Discontinuation	28-day Follow-Up	Details in Section
Visit	1	2	3	4	5	5	6	7	8	9	10+					
Day	-28 to -1	D1	D2	D3	D4	D6	D1	D8	D9	D15	D1	D2				
Window (Days)		0	0	0	0	0	0	0	0	0	±7	0	±7	0	±7	
Informed Consent	Х															4
Demography & baseline characteristics	Х															6.3.1
Medical/surgical history	Х															6.3.1
Inclusion/Exclusion Criteria	Х															4
Physical Examination	Х	Х					Х				Х		Х	X		6.3.2
WHO Performance Status	Х	Х					Х				Х		Х	Х		6.3.2
Pregnancy Test (pre- menopausal females only)	X															6.3.5
Ophthalmologic assessment	Х	•	As clinically indicated								6.3.6					
Vital Signs	X	X	Х				X	X	X	X	X	Х	Х	X		6.3.3
Height	X															6.3.3

Weight	Х	Х					Х				Х		Х	X		6.3.3
ClinicalChemistry/Hae matology/Urinalysis	X	X					Х	Х		X	X		X	X		6.3.5
ECG	Х	Х					Х				Х		Х	X		6.3.4
Echo/MUGA	X	-				1	2 week	dy(±1	week)	relativ	ve to first d	ose				6.3.7
PK blood samples (including metabolites)		X	X	X	X	X	X	X	X	X	X (Cycle 2 only)	X				6.5.1
RECIST assessments	X ^(b)						•	Every	y 6 we	eks(±1	week) ^(c)					6.7.1
Dispense Study Medication		X					X				X		X			5
Dose with AZD9291		Х					•	-		Da	aily dosing					5
Concomitant Medication	•			·	·									· · ·	•	4.3.1
Adverse Events ^(d,e)	•														►	6.4

(a) If assessments were performed within 7 days prior to the first dose of study treatment and the patient meets the eligibility criteria, these assessments do not need to be repeated during visit 2.

(b) This assessment does not need to be repeated if it is performed within 28 days prior to the start of study treatment, unless the investigator has a reason to believe that there has been a change in the patient's tumour burden. If imaging is repeated before the start of study treatment, the most recent assessment would then be recorded as the screening tumour assessment.

(c) RECIST assessments should be performed every 6 weeks (\pm 7 days) from visit 6(C1D1).

(d) Following AZD9291 discontinuation, SAEs considered related to study procedures should continue to be collected

(e) Continued to collect unresolved AEs post 28-day Follow-up visit (if applicable).

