Any AE occurring within the defined 28 day follow-up period after discontinuation of investigational product will be included in the AE summaries. Any adverse events in this period that occur after a patient has received further therapy for cancer (following discontinuation of investigational product) will be flagged in the data listings. AEs occurring after the 28 day follow-up period after discontinuation of investigational product will be listed separately, but not included in the summaries.

Haematology, clinical chemistry, vital signs, ECG data, ophthalmic examination data, demographic data and concomitant medications will be listed individually by patient and suitably summarised. For all laboratory variables, which are included in the current version of CTCAE, the CTCAE grade will be calculated. Summary statistics of mean, median, standard deviation, minimum, maximum and number of observations will be used.

Details of any deaths will be listed for all patients.

Any qualitative assessments will be summarised for all patients using the number of patients with results of negative, trace or positive.

Graphical presentations of safety data will be presented as is deemed appropriate. This may include, but is not restricted to, presentation of parameters against time, concentration or shift plots. Appropriate scatter plots will also be considered to investigate trends in parameters compared to baseline.

Pharmacokinetics

Plasma concentrations of AZD9291, AZ5104 and AZ7550 will be summarised by nominal sample time. Plasma concentrations and derived PK parameters will be summarised by dose level. Parameters following single and multiple dosing will be summarised separately. Plasma concentrations at each time point will be summarised according to dose by the following summary statistics:

- The geometric mean (gmean, calculated as $\exp [\mu]$, where μ is the mean of the data on a logarithmic scale)
- Coefficient of variation (CV, calculated as $100 \sqrt{[exp(s2)-1]}$, where s is the standard deviation of the data on a log scale)
- Gmean \pm standard deviation (calculated as exp[$\mu \pm$ s])
- Arithmetic mean calculated using untransformed data
- Standard Deviation calculated using untransformed data
- Minimum
- Maximum
- Number of observations

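### Table 3 stops new-AE collection at a follow-up contact that Table 2 allows from Day 21, while the text of Section 6.4.3 and Section 7.7 run to Day 28

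*Protocol*

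**What the plan says.** Four places in the protocol bear on when post-treatment AE collection ends.

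- **Section 6.4.3, text.** "AEs will be collected throughout the study, from informed consent until the end of the follow up period". The end of that period is then fixed: "The follow-up period is defined as 28 days after study treatment is discontinued".
- **Section 6.4.3, Table 3.** The middle column runs up to the 28-day follow-up visit and is labelled "safety follow-up period". The row for new events reads "Collect all new AEs in eCRF Yes Yes No", so the entry after the visit is No. The row for deaths due to an AE or of unknown cause has the same pattern.
- **Section 6.1, Table 2, and Section 6.3.8.2.** The last entry of the window row, under "28-day Follow-Up", is ±7 days. Section 6.3.8.2 sets the minimum form of the contact: "telephone contact should be made with the patient 28 days following the discontinuation of AZD9291". It states no window and refers to Table 2.
- **Section 7.7, Safety.** "Any AE occurring within the defined 28 day follow-up period after discontinuation of investigational product will be included in the AE summaries". Later events are handled apart: "AEs occurring after the 28 day follow-up period after discontinuation of investigational product will be listed separately, but not included in the summaries".

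**The concern.** One term, the safety follow-up period, has two end points. In the text of Section 6.4.3 and in Section 7.7 the end is a fixed day, 28 days after stopping. In Table 3 it is the date of a contact, and Table 2 lets that date move by a week either way.

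The two halves of the window do not matter equally. A late contact covers the whole defined period, and Section 7.7 keeps anything after Day 28 out of the summaries. An early contact cannot ask about days that have not yet happened. Section 6.4.3 treats this contact as the patient's last visit, so no later scheduled enquiry closes the gap. A site working from Tables 2 and 3 could call on Day 21, stop entering new AEs, and be within schedule while falling short of the text.

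At stake is the completeness of the AE data after treatment. Safety and tolerability is the key secondary objective (Section 7.2). The summary would treat every discontinued patient as observed for 28 days, when actual coverage depends on when the site made contact.

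**Working it through.** **Inputs**

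- Defined follow-up period: 28 days after discontinuation (Section 6.4.3).
- Window for the follow-up contact: ±7 days (Table 2).
- New-AE collection after the contact: No (Table 3).
- Summary period: onset within the 28 days (Section 7.7).

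**Step 1. Does the ±7 belong to the follow-up column?** The Table 2 window row, read across the columns, gives: screening blank; nine zeros (Cycle 0 Days 1, 2, 3, 4 and 6; Cycle 1 Days 1, 8, 9 and 15); ±7 (Day 1 of Cycles 2 to 4); 0 (Cycle 2 Day 2); ±7 (Cycle 5 onwards); 0 (discontinuation); ±7 (28-day follow-up); and a blank for the section reference. That is 16 entries for 16 columns, so the mapping is unambiguous.

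**Step 2. Permitted contact days.** Earliest: 28 − 7 = Day 21. Latest: 28 + 7 = Day 35.

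**Step 3. Days without a scheduled AE enquiry.** If collection stops at a contact on day d, the uncovered days are max(0, 28 − d) and the uncovered share is that number divided by 28.

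| Contact day | Uncovered days | Share of the 28 days |
|---|---|---|
| 21 | 7 | 7/28 = 25.0% |
| 24 | 4 | 4/28 = 14.3% |
| 28 | 0 | 0% |
| 35 | 0 | 0% (Days 29 to 35 listed, not summarised) |

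The stated 28 days is guaranteed only when d is 28 or more. The shortest period that Tables 2 and 3 allow is 21 days.

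**Step 4. A less extreme illustration.** Assume contacts fall evenly on the 15 days from 21 to 35. The document does not say this. The mean loss is (7 + 6 + 5 + 4 + 3 + 2 + 1 + 8 × 0)/15 = 28/15 = 1.9 days, and 1.87/28 = 6.7%.

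**Step 5. Scale against all AE observation.** Take a patient who stops at the end of Cycle 4. From first dose there are 7 + 4 × 21 = 91 days, plus 28 of follow-up, which makes 119. Seven lost days are 7/119 = 5.9% of that span, and less for longer treatment.

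**Step 6. After the fix.** With a window of 0/+7, d is at least 28 and the uncovered days are 0 of 28.

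**The case against.** The strongest reply is that the text of Section 6.4.3 already requires collection for 28 days. Table 3 is only a summary, and its middle column carries the label that the text equates with 28 days. Deaths within the follow-up period must also be reported under the same section. On that reading nothing shortens the period. This stands in part: the fault is a conflict between the text and the tables, and a reader who infers that the protocol sets a 21-day safety period goes too far. The conflict still has an effect, because the tables define both the schedule and the cut-off, and following them can miss what the text requires.

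Other routes also catch some late events. Spontaneous reports are recorded, procedure-related SAEs are still collected after the visit, unresolved AEs are followed, and SAEs that the investigator learns of and considers related to AZD9291 must be notified. Patients without progression return for tumour assessments (Section 6.7.1). It would therefore be wrong to say that Days 22 to 28 are simply unobserved or that SAEs are generally lost. What lacks a prompted route is a new non-serious AE, or an SAE judged unrelated or not learned of. Return visits do not close that gap, because Table 3 still says No to new AEs.

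It is tempting to read the 25% as a quarter of AE data lost, or as bias in a post-treatment incidence rate. The document supports neither. Section 7.7 says that safety data are not formally analysed, combines all cycles and adds the 28-day tail. It specifies no separate post-treatment rate. Nor need all 24 patients be affected: some may still be on treatment at the final cut-off, and after the final lock Section 6.4.3 sets a limited collection (mainly SAEs and deaths) for 28 days after last dose without tying it to a visit.

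Leaving the matter to an analysis plan does not help, since analysis cannot recover events that were never collected.

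**Conclusion.** The point holds as a conflict between the text of Section 6.4.3 and Section 7.7 on one side and Tables 2 and 3 on the other, and it should be corrected. The worst case is 7 of 28 post-treatment days (25% of the tail) without a scheduled AE enquiry, for a patient contacted on Day 21. Under evenly spread contacts the mean is about 1.9 days (6.7%). Both figures assume that the site stops entering new AEs at the contact, as Table 3 directs. Neither is an estimate of events lost, which would need an onset pattern that the document does not give.

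With about 12 patients per cohort, one missed event would move a cohort's incidence of that AE by 1/12, or about 8 percentage points, if the patient had not already had it. The effect is confined to the completeness of descriptive safety summaries. The primary PK analysis is untouched.

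**What to change.** Reconcile Table 2, Section 6.3.8.2, Section 6.4.3 with Table 3, and Section 7.7:

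1. In Table 2, change the window of the 28-day follow-up from ±7 days to 0/+7 days, and let Section 6.3.8.2 carry the same window.
2. In Table 3, head the middle column *until 28 days after discontinuation, as ascertained at a contact on or after Day 28*, and begin the last column after that point. This also settles the row for deaths.
3. Keep the Section 7.7 summary limited to onset within 28 days, so that contacts up to Day 35 do not inflate it.

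The cost is one window entry, its repetition in Section 6.3.8.2 and the column headings. There is no extra visit or procedure. Sites lose the option of calling early. Rewording Table 3 alone would remove the contradiction on paper but would still leave an early call as the last scheduled enquiry, so the window should change too.
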